7.3.1. Study Duration, Treatment Compliance, and Exposure

Two summary tables of the extent of exposure to ALXN1210 will be presented. The duration on treatment (in weeks), the number of infusions, and the total dose (in mg) through the first 26 weeks (ie, Initial Evaluation Period) will be summarized using descriptive statistics. In addition, a similar table will be produced for exposure throughout the entire study.

7.3.2. Adverse Events (AEs)

The following definitions will be used for AEs:

- Pretreatment adverse events: Any AE that starts after providing informed consent, but before the first infusion of study drug
- Treatment-emergent adverse event: Any AE that starts during or after the first infusion of study drug.
- Treatment-emergent SAE: A treatment-emergent AE (TEAE) that is serious.

PreTreatment Adverse Events will be summarized in listings and Treatment-Emergent Adverse Events will be tabulated and presented as described below.

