7.1. Summary of Study Design

Study ALXN1210-aHUS-311 is a Phase 3, open-label, single arm, multicenter study to evaluate the safety and efficacy of ALXN1210 administered by intravenous (IV) infusion to adolescent (12 to < 18 years of age) and adult (≥ 18 years of age) patients with aHUS. The study will enroll approximately 55 patients to receive ALXN1210. All patients must be naïve to complement inhibitor treatment and include at least 6 and up to 10 adolescent (12 to < 18 years of age at Screening) patients and at least 10 and up to 25 patients with prior kidney transplants. A minimum of 30 patients who meet all laboratory criteria for TMA (platelet count of < 150,000 per microliter, LDH $\geq 1.5 \times$ upper limit of normal (ULN), hemoglobin \leq lower limit of normal (LLN), and serum creatinine level \geq ULN) as determined by the central laboratory at Day 1, will be enrolled.

The study consists of an up to 7 day Screening Period, a 26-week Initial Evaluation Period, and an Extension Period until the product is registered or approved (in accordance with country-specific regulations) or for up to 4.5 years, whichever occurs first. Dosages are based on the patient's body weight recorded at the last visit or more recently (Table 6). Patients will receive a loading dose of ALXN1210 IV (2400 mg for patients weighing ≥ 40 to < 60 kg, 2700 mg for patients weighing ≥ 60 to < 100 kg, 3000 mg for patients weighing ≥ 100 kg) on Day 1, followed by maintenance doses of ALXN1210 IV (3000 mg for patients weighing ≥ 40 to < 60 kg, 3300 mg for patients weighing ≥ 60 to < 100 kg, 3600 mg for patients weighing ≥ 100 kg) on Day 15 and once every 8 weeks (q8w) thereafter for a total of 26 weeks of treatment in the Initial Evaluation Period followed by maintenance doses q8w in the Extension Period (Figure 1). The end of trial is defined as the last patient's last visit.

Figure 1 illustrates the study design.

Figure 1: Study Design Schematic for Clinical Protocol ALXN1210-aHUS-311

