9.8. Vaccination

Due to its mechanism of action, the use of ALXN1210 increases the patient's susceptibility to infection. To reduce the risk of infection, all patients must be vaccinated against *N. meningitidis*.

Patients must be vaccinated against *N. meningitidis* within 3 years prior to, or at the time of, receiving the first dose of ALXN1210. Patients who will be treated with drug less than 2 weeks after receiving a meningococcal vaccine must receive treatment with appropriate prophylactic antibiotics until 2 weeks after vaccination. Vaccines against serotypes A, C, Y, W135, and B, where available, are recommended to prevent common pathogenic meningococcal serotypes. Patients must be vaccinated or revaccinated according to current national vaccination guidelines or local practice for vaccination use with complement inhibitors (eg, eculizumab).

It is recognized that some patients who have not been vaccinated against *N. meningitidis* within 3 years prior to receiving the first dose of ALXN1210 may not be able to receive a vaccination at the time of the first dose. Patients who have not been vaccinated prior to initiating ALXN1210 treatment should receive prophylactic antibiotics prior to and for at least 2 weeks after meningococcal vaccination.

Vaccination may not be sufficient to prevent meningococcal infection. Consideration should be given per official guidance and local practice on the appropriate use of antibacterial agents. All patients should be monitored for early signs of meningococcal infection, evaluated immediately if infection is suspected, and treated with appropriate antibiotics, if necessary.

To increase risk awareness and promote quick disclosure of any potential signs or symptoms of infection experienced by the patients during the course of the study, patients will be provided a safety card to carry with them at all times and for 8 months after last dose of ALXN1210.

Additional discussion and explanation of the potential risks, signs, and symptoms will occur at specific time points as part of the review of the patient safety card and throughout the study as described in the Schedule of Assessments (Table 1, Table 2, and Table 3).

Patients < 18 years of age must also be vaccinated against *Haemophilus influenzae* type b (Hib) and *Streptococcus pneumoniae* according to national and local vaccination schedule guidelines, prior to, or at the time of, receiving the first dose of ALXN1210.

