For patients who discontinue ALXN1210 treatment, but remain in study, their data will be summarized along with data from patients remaining on treatment for 8 weeks (56 days) after their last dose of study drug. Data beyond this point will be presented in separate supplemental listings strictly limited to these patients. If such patients start retreatment with ALXN1210, their data from the time of study treatment restart will also be presented in separate supplemental listings limited to patients who will have restarted study treatment. However, data on AE, concomitant medications, and nonpharmacologic therapies and procedures from the time of treatment restart will be considered treatment emergent or concomitant, and will be summarized as such, combined with data from patients who remained on treatment throughout the study.

Pharmacokinetic/PD and ADA data from patients who discontinue ALXN1210 treatment, but remain in study, will be summarized along with data from patients remaining on treatment, until 8 weeks after their last dose of study drug. Data beyond this point will be presented in separate supplemental listings limited to these patients. If such patients start retreatment with ALXN1210, their PK/PD and ADA data from the time of study treatment restart will also be presented in separate supplemental listings limited to patients who will have restarted study treatment.

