15.9.1. Adverse Events

The following definitions will be used for AEs:

- Pretreatment adverse events: Any AE that starts after providing informed consent, but before the first infusion of study drug
- Treatment-emergent adverse event: Any AE that starts during or after the first infusion of study drug. Adverse events that start 56 days or later after the last dose of study drug will not be considered as treatment emergent.
- Treatment-emergent SAE: A treatment-emergent AE (TEAE) that is serious ([Section 11.7.4](#) for definitions).

The incidence of TEAEs, TEAEs leading to withdrawal from the study, TEAEs leading to study treatment discontinuation, drug-related TEAEs, TEAEs during study drug administration, severe TEAEs, and SAEs will be summarized. All AEs will be coded using MedDRA version 18 or higher, and will be summarized by system organ class (SOC) and PT overall, by severity, and by relationship to treatment. Detailed by-patient listings of TEAEs, SAEs, related TEAEs, TEAEs during study drug administration, TEAEs leading to withdrawal from the study, and TEAEs leading to study treatment discontinuation will be provided.

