4.3. Planned Analyses

An interim analysis is planned for this study at the end of the 26-week Initial Evaluation Period after all patients have completed or withdrawn from the 26-week Initial Evaluation Period. This analysis will allow for evaluation of the primary endpoint and will be the basis for the initial clinical study report (CSR).

The final analysis which will summarize long-term efficacy, safety, and PK parameters will be performed at the end of the 2-year Extension Period.

The present document serves to describe both of these planned analyses.

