5.2.1. Adverse Events

Treatment-emergent AEs (TEAEs) are defined as any event not present prior to exposure to Investigational Product or any event already present that worsens in either intensity or frequency following exposure to Investigational Product. An AE will be considered a TEAE if the start date and time is on or after the start date and time of the first study drug infusion. All other AEs are considered PreTreatment Adverse Events (PTAEs).

The severity of AEs will be graded using Common Terminology Criteria for Adverse Events (CTCAE) version 4.03 or higher. A grading (severity) scale is provided for each AE term. Each LLT will be coded to a MedDRA preferred term.

Grade refers to the severity of the AE. The CTCAE assigns a grade of 1 through 5, with unique clinical descriptions of severity for each AE (Table 2).

Table 2: Adverse Event Severity Grading Scale

Grade	Description
Grade 1	Mild; asymptomatic or mild symptoms; clinical or diagnostic observations only; intervention not indicated
Grade 2	Moderate; minimal, local or noninvasive intervention indicated; limiting age-appropriate instrumental activities of daily living (ADL) ^a
Grade 3	Severe or medically significant, but not immediately life-threatening; hospitalization or prolongation of hospitalization indicated; disabling; limiting self-care ADL ^b
Grade 4	Life-threatening consequences; urgent intervention indicated.
Grade 5	Death related to AE.

Abbreviations: ADL = activities of daily living; AE = adverse event

^a Instrumental ADL refers to preparing meals, shopping for groceries or clothes, using the telephone, managing money, etc.

^b Self-care ADL refers to bathing, dressing and undressing, feeding self, using the toilet, taking medications, and not bedridden.

An Investigator must provide a causality assessment (Unrelated, Unlikely, Possible, Probable, or Definite) for all AEs (both serious and nonserious) based upon the Investigator's medical judgment and the observed symptoms associated with the event (Table 3).

Table 3: Causality Assessment Descriptions

Assessment	Description
Not Related/Unrelated	Suggests that there is no causal association between the investigational product and the reported event.

Assessment	Description

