9.4.6. Adverse Events

The analysis of Adverse Events is described in detail in [Section 7.3.2](#).

Treatment-emergent AEs (TEAEs) are events with start dates and start times on or after the date and time of the first study drug dose. If the start date of an AE is partially or completely missing and the end (stop) date and time of the AE does not indicate that it occurred prior to first dose, then the determination of treatment-emergent status will be based on the following:

- If the start year is after the year of the first study drug dose, then the AE is treatment-emergent; else,

- If the start year is the same as the year of the first study drug dose and
 - the start month is missing, then the AE is treatment emergent; else if
 - the start month is present and is the same or after the month of the first study drug dose, then the AE is treatment-emergent; else,
- If the start date is completely missing, then the AE is treatment-emergent.

All other AEs are considered PreTreatment Adverse Events (PTAEs).

Related AEs are defined as possible, probable or definitely related. Unrelated AEs are defined as unlikely or not related.

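### The SAP sets no end to treatment-emergent status and omits the protocol's rule for off-drug data, and both documents keep a 2-year Extension that the current protocol has outgrown

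*SAP*

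**What the plan says.** **Treatment-emergent AEs.** SAP 7.3.2 gives only a lower bound: "Any AE that starts during or after the first infusion of study drug". The derivation in SAP 9.4.6 repeats it: "events with start dates and start times on or after the date and time of the first study drug dose". Both SAP 5.2.1 and 9.4.6 assign every remaining AE to the pretreatment class, so no post-treatment class exists. Protocol 15.9.1 has the same lower bound and then adds: "Adverse events that start 56 days or later after the last dose of study drug will not be considered as treatment emergent".

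**Other data after stopping drug.** Protocol 15.1 summarizes data from patients who stop drug but stay in study with everyone else's for 56 days after the last dose. After that: "Data beyond this point will be presented in separate supplemental listings strictly limited to these patients". Data after retreatment are also listed separately, except that AEs, concomitant medications and procedures from the restart count as treatment-emergent or concomitant and are pooled. The SAP has no counterpart to any of this.

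**Timing of the final analysis.** SAP 4.3 has it "performed at the end of the 2-year Extension Period", and protocol 15.13 uses the same 2-year period for its second analysis. Protocol 7.1 runs the Extension until registration or approval "or for up to 4.5 years, whichever occurs first", Table 3 schedules visits to Day 1863, and protocol 15.1 plans a final CSR at study completion.

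**Declared departures.** SAP 4.1 states that there are none.

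**The concern.** The two documents give different TEAE tables for the same database. Protocol 8.3.2 lets a patient stop drug and attend visits to Day 1863, and protocol 11.7.6.1 keeps collecting that patient's AEs until the last visit. The disputed events will therefore be on file. A programmer working from the SAP would count them as treatment-emergent; a reader working from the protocol would expect them to be excluded. Because the SAP declares no departure, nothing warns either of them.

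The same patients can enter the long-term efficacy and laboratory summaries. SAP 9.4.4 builds those on the protocol's visit schedule. The SAP's value exclusions cover table top hemolysis (5.2.3), dialysis (9.4.9) and transfusion (9.4.10), but not time off drug. SAP 7.2.2.2 censors non-responders at the last visit or study discontinuation, not at treatment discontinuation, so off-drug time counts in the time-to-response analysis.

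The 2-year label leaves it unclear whether the SAP's final analysis covers the later part of the Extension.

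**Working it through.** **1. The Extension length, reproduced.** The Extension starts with the Day 183 dose and the last scheduled visit is Day 1863 (protocol Tables 2 and 3).
- 1863 − 183 = 1,680 days = 240 weeks; 1,680 / 365.25 = 4.60 years. To Day 1807 it is 1,624 / 365.25 = 4.45 years. The stated 4.5 years fits the schedule.
- For 2 years: 183 + 2 × 365.25 = Day 913.5. The nearest visit is Day 911, where Table 2 ends: 911 − 183 = 728 days = 104 weeks = 1.99 years.

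**2. What lies beyond the 2-year point.**
- Visits after Day 183, every 56 days: 1,680 / 56 = 30.
- Visits after Day 911: (1863 − 911) / 56 = 952 / 56 = 17.
- Share: 17 / 30 = 57%, covering 952 days (2.6 years).

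**3. The rules side by side.**

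| AE starts | Protocol 15.9.1 and 15.1 | SAP 5.2.1, 7.3.2, 9.4.6 |
|---|---|---|
| Before first infusion | Pretreatment | Pretreatment |
| First infusion to under 56 days after last dose | TEAE | TEAE |
| 56 days or more after last dose, no restart | Not TEAE | TEAE |
| After retreatment starts | TEAE | TEAE |

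One case needs care when the texts are aligned. Protocol 15.9.1 refers to the last dose without saying which course of treatment it means. In a retreated patient, an AE in the gap between day 56 off drug and the restart precedes the final dose, so copying that sentence alone would not settle its class.

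**4. Length of the post-dose window for a patient followed off drug to Day 1863.** Under the protocol it is 56 days. Under the SAP it is 1863 minus the day of the last dose:
- last dose Day 127: 1,736 days (31 × 56)
- last dose Day 183: 1,680 days (30 × 56)
- last dose Day 911: 952 days (17 × 56)
- last dose Day 1807: 56 days, so essentially no difference for a patient dosed on schedule.

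For the Day 183 case, the time beyond the cut-off is 1863 − (183 + 56) = 1,624 days, and 1,624 / 1,863 = 87% of that patient's study time.

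**5. Share of study person-time (assumed counts).** The documents do not give the number of patients who stop drug and stay. Assume k of 55 patients are last dosed on Day 183 and never retreated, with all 55 followed to Day 1863. The share beyond the cut-off is k × 1,624 / (55 × 1,863) = k × 1,624 / 102,465:
- k = 1: 1.6%
- k = 3: 4.8%
- k = 5: 7.9%

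This is person-time, not a count of AEs.

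**The case against.** **Version lag.** The latest protocol amendment that the SAP cites is Amendment 3 of July 2017, and SAP 5.1.2 lacks the protocol's secondary endpoint on TMA parameters after discontinuation. The mismatch therefore looks like a missing update rather than a chosen analysis. That is probably right, but it does not remove the conflict: SAP 4.3 says the document describes both planned analyses.

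**Silence is not a pooling rule.** A reader might infer that the SAP prescribes pooling of off-drug efficacy and laboratory values. It never says so; it refers to the protocol for further detail, and protocol 15.1 could be read as still governing. This stands in part. The AE conflict is explicit, whereas for other data the point is that no SAP rule removes them. PK/PD is not an SAP omission at all, because SAP 7.2.5 leaves it to a separate plan.

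**Late meningococcal infections.** Patients carry the safety card "for 8 months after last dose of ALXN1210", well past 56 days, so a reader might infer that the protocol's cut-off would hide late cases. The documents do not support that. SAP 7.3.2.5 provides a separate table and listing of meningococcal AEs, and SAP 9.4.7 searches the whole AE dataset with no time limit, plus a medical review.

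**No long-term analysis.** A reader might also infer that follow-up after Day 911 has no planned analysis. Protocol 15.1 plans the final CSR at study completion, protocol 6.2.2 measures the secondary endpoints over the entire study, and SAP 7.3.1 tabulates exposure for the entire study. Protocol 15.13 calls its item a second analysis, which need not replace that CSR. The defect is an outdated duration.

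**Few patients.** Early terminators get a follow-up call about 56 days after the last dose, and the Extension may end early on approval. The effect is thus confined mainly to patients who stop drug and remain in study. This stands, and it limits the size.

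**Conclusion.** The point holds. The TEAE window is a direct contradiction between the SAP and protocol 15.9.1. The missing off-drug rule is an omission that permits pooling which protocol 15.1 rules out. The 2-year Extension in SAP 4 and 4.3 and protocol 15.13 disagrees with protocol 7.1, 9.2 and Table 3, so the protocol also disagrees with itself.

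For an affected patient the difference is large: up to 30 times the protocol's window if the last dose is on Day 183. For the study it is unknown. The 1.6% to 7.9% range rests on 1 to 5 assumed patients in a constructed worst case, with no retreatment and full follow-up to Day 1863. The 26-week primary endpoint does not use the TEAE definition. The matter affects long-term safety and efficacy reporting, and is worth correcting before the final analysis.

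**What to change.** 1. Put the protocol 15.9.1 cut-off and the protocol 15.1 retreatment rule for AEs into SAP 5.2.1, 7.3.2 and 9.4.6. Add a post-treatment AE class that expressly includes AEs between day 56 off drug and any restart.
2. Put the protocol 15.1 rule for other off-drug and retreatment data into the SAP efficacy and safety sections, including immunogenicity, and state how it applies to censoring in SAP 7.2.2.2. The PK/PD part belongs in its separate plan.
3. Reconcile the Extension length in SAP 4 and 4.3 and protocol 15.13 with protocol 7.1, and place the final analysis at study completion.
4. Correct SAP 4.1, or have it list any departure that is intended.
5. When the cut-off goes in, keep the meningococcal table on all AEs regardless of timing, as SAP 7.3.2.5 and 9.4.7 already provide. A table of AEs from 56 days to 8 months after the last dose, in patients still on study, would be optional.

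The cost is SAP amendment wording, a one-line protocol correction and the programming of one extra AE class. No new data are needed.

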7.3.2.1. Overall Summary of Adverse Events

An overall summary of AEs and SAEs will be presented. The number of events (n), and number and percentage of patients with events (n, %) will be shown for the following event subcategories:

Table 4: Adverse Events (AEs) and Serious AEs

Relationship	Severity: Toxicity Grade
Related AEs (Possibly, Probably, or Definitely Related)	Grade 1
Not Related AEs (Not Related or Unlikely Related)	Grade 2
	Grade 3
	Grade 4
	Grade 5

Fatal TEAEs, TEAEs resulting in study treatment discontinuation, TEAEs resulting in withdrawal from the study, and TEAEs that start during study drug administration will also be included in this overall summary. These statistics will be prepared separately for all AEs and SAEs.

Detailed listings of all AEs, SAEs, and related AEs, will be presented. These listings will include severity and relationship to treatment, as well as action taken regarding study treatment, other action taken, and AE outcome.

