- ^f Abbreviated physical examination consists of a body system relevant examination based upon Investigator judgment and patient symptoms. At least 1 body system must be checked for an abbreviated examination.
- ^g Vital sign measurements will be taken after the patient has been resting for at least 5 minutes and will include systolic and diastolic BP (millimeters of mercury [mm Hg]), pulse oximetry, heart rate (beats/minute), respiratory rate (breaths/minute), and temperature (degrees Celsius [$^{\circ}$ C] or degrees Fahrenheit [$^{\circ}$ F]). On dosing days, vital signs will be taken predose.
- ^h Single 12-lead ECG will be collected at Screening, Day 57, and predose on Day 183 and any time on the ET visit day. Patients must be supine for approximately 5 to 10 minutes before ECG collection and remain supine but awake during ECG collection.
- ⁱ Clinical safety laboratory measurements will be collected predose on dosing days. LDH for eligibility will be determined from the chemistry assessment. Follicle-stimulating hormone levels will be measured during Screening only in order to confirm postmenopausal status.
- ^j Serum sample for LDH isozyme testing will only be collected at selected sites at any/all timepoints prior to ALXN1210 dosing, dependent on sample testing availability.
- ^k Assessment for safety, as well as the primary and secondary endpoints.
- ^l Serum samples for PK/PD analyses will be collected at the indicated visits. For indicated visits falling on dosing days, samples will be collected predose (within 0.5 hours prior to the start of infusion) and at end of infusion (EOI) (within 0.5 hours after the EOI from the patient's opposite, noninfused arm). In order to minimize needle sticks to the patient, the predose sample may be drawn through the venous access created for the dose infusion, prior to administration of the dose. As noted, the postdose sample must be drawn from the opposite, noninfused arm. For indicated visits not falling on dosing days, samples may be collected at any time that visit day. All collection times will be recorded in the eCRF.
- ^m Collection will be predose on days of dosing and for days without dosing, at any time that visit day. All collection times will be recorded in the eCRF.
- ⁿ Collection will be predose. All collection times will be recorded in the eCRF.
- ^o Collection will be predose and combined with urine stabilizing buffer. All collection times will be recorded in the eCRF.

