9.5. Special Treatment Considerations

Infusion of other monoclonal antibodies has been associated with infusion reactions, with onset typically during or shortly after completion of the infusion. Please refer to Appendix C for guidance on identifying and managing potential drug infusion reactions.

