APPENDIX C. MANAGEMENT OF POTENTIAL DRUG INFUSION REACTIONS

Infusion of other monoclonal antibodies has been associated with infusion reactions, with onset typically during or shortly after completion of the infusion. For this reason, patients will be carefully observed during each infusion.

Patients who develop AEs of rash, hives, itching, or dysphagia of mild to moderate intensity during their infusion of ALXN1210 may continue to receive the infusion if deemed to be medically appropriate by the Investigator. Medical intervention may include, but is not limited to, slowing of the infusion rate (with or without treatment) or interrupting or stopping the infusion.

Any acute reaction should be treated according to standard medical practice depending upon clinical signs and symptoms. If a patient requires medical intervention, the patient should remain at the investigational site until his or her condition stabilizes. The AE and any associated concomitant medications must be captured on the patient's source document and eCRF.

Some patients treated with IV infusions of monoclonal antibodies have experienced concurrent reactions with signs or symptoms that can be classified as acute allergic reactions/hypersensitivity reactions or cytokine release syndrome. Signs and symptoms include headache, fever, facial flushing, pruritus, myalgia, nausea, chest tightness, dyspnea, vomiting, erythema, abdominal discomfort, diaphoresis, shivers, hypertension, lightheadedness, hypotension, palpitations, and somnolence. Anaphylaxis might occur at any time during an infusion; therefore, patients will be monitored closely during the infusion. In addition, the re-administration of some monoclonal antibodies has been associated with serum sickness-like reactions manifesting 1 to 14 days after drug administration. All AEs that may indicate an infusion-related response will be graded according to CTCAE Version 4.03 or higher.

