7.3.2.5. Deaths, Other SAEs, and Other Significant Adverse Events

Individual listings will be presented for AEs leading to study treatment discontinuation, AEs leading to withdrawal from the study, AEs starting during study drug administration, and fatal AEs.

In addition, a summary table and a listing of AEs related to meningococcal infections will be provided. See [Section 9.4.7](#) for a list of AE preferred terms that will be considered for these summaries of meningococcal infections.

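### The only adverse event outputs tied to dosing time stop at the end of the infusion, and nothing groups the infusion-related or serum sickness-like reactions that start later

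*SAP*

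**What the plan says.** Three places define an adverse event output by its timing relative to dosing, and they use the same restriction.

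- SAP 7.3.2.1, overall summary: "TEAEs that start during study drug administration will also be included in this overall summary".
- SAP 7.3.2.5, individual listings: "AEs starting during study drug administration".
- Protocol 15.9.1: "TEAEs during study drug administration, severe TEAEs, and SAEs will be summarized".

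The protocol's account of when these reactions begin is wider. Section 9.5 and Appendix C describe infusion reactions to other monoclonal antibodies "with onset typically during or shortly after completion of the infusion". Appendix C adds that re-administration of some monoclonal antibodies "has been associated with serum sickness-like reactions manifesting 1 to 14 days after drug administration". Protocol 8.3.2 uses the same 1-to-14-day interval when it makes a serum sickness-like reaction a reason for permanent treatment discontinuation. Appendix C also requires adverse events that may indicate an infusion-related response to be graded by CTCAE.

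The SAP names one event of special interest, meningococcal infection (5.2.7). It has its own preferred-term search with medical review (9.4.7), a summary table and a listing (7.3.2.5).

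**The concern.** The protocol names two onset periods that lie after the infusion, and the SAP has no output for either. A hypersensitivity reaction that starts soon after the pump stops, or a rash with fever a week after a dose, falls outside the during-administration row and listing. If reported as symptoms, it is spread over several preferred terms in the general tables, and no table shows how long after dosing it began.

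This matters because the trial has a single arm. With no control group, timing relative to the infusion is an important part of the evidence that separates a drug reaction from background illness. A reader looking for infusion-associated harm would naturally turn to the one row defined by dosing time, and a low count there could reassure more than it should.

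Other scheduled data help little. For vital signs, "On dosing days, vital signs will be taken predose", and protocol 11.4 has laboratory samples taken before each administration. In the Extension Period, scheduled visits are 56 days apart and coincide with dosing, so none falls within the 14 days after an infusion. Adverse event reports are then the main source, which makes their tabulation more important.

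**Working it through.** The plan states no figure on this point, so there is nothing to reproduce. The check compares the text first and then adds arithmetic for scale.

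**1. Onset periods against planned outputs**

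| Reaction | Onset given in the protocol | In the during-administration row? |
|---|---|---|
| Infusion reaction | During the infusion (9.5, Appendix C) | Yes |
| Infusion reaction | Shortly after the infusion (9.5, Appendix C) | No |
| Serum sickness-like reaction | 1 to 14 days after dosing (8.3.2, Appendix C) | No, unless onset happens to coincide with the next infusion |

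**2. Other outputs that might cover the gap**

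- Tables by system organ class and preferred term, by relationship and by severity (SAP 7.3.2.2 to 7.3.2.4) include every treatment-emergent event whatever its time since dosing. None is split by that time.
- Events that end treatment are counted and listed (SAP 7.3.2.1, 7.3.2.5), but not by type of reaction.
- Neither document contains an infusion-reaction or hypersensitivity term list, an investigator flag for such reactions, or a post-infusion window.

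**3. Clock time covered**

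The minimum infusion durations in protocol Table 5 run from 102 to 140 minutes. Fourteen days is 14 × 24 × 60 = 20,160 minutes.

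- 102 / 20,160 = 0.51%
- 140 / 20,160 = 0.69%

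This is a share of time, not of events. Infusion reactions cluster around the infusion, and the 14-day interval belongs only to serum sickness-like reactions.

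**4. What the row might show (illustration only)**

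Take N = 55, the planned enrolment. Let r be the true proportion of patients affected and s the share of those whose reaction starts during an infusion. The documents give neither r nor s; both are assumptions. The expected count in the row is N·r·s, and P(row = 0) = (1 − r·s)^N.

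| r | s | Expected, all reactions (N·r) | Expected in row (N·r·s) | P(row = 0) |
|---|---|---|---|---|
| 5% | 25% | 2.75 | 0.69 | 50% |
| 5% | 50% | 2.75 | 1.38 | 25% |
| 5% | 100% | 2.75 | 2.75 | 6% |
| 10% | 25% | 5.5 | 1.38 | 25% |
| 10% | 50% | 5.5 | 2.75 | 6% |
| 10% | 100% | 5.5 | 5.5 | 0.3% |

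For the first line, 1 − 0.05 × 0.25 = 0.9875, and 0.9875^55 = 0.50. The s = 100% lines show the result if every affected patient were counted.

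**5. Why a time window alone would not do**

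Four doses in the Initial Evaluation Period give 4 × 14 = 56 days out of 182, or 31%. In the Extension Period the share is 14 / 56 = 25%. A window applied to all adverse events would collect many unrelated ones, so it needs a term-based grouping as well.

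**The case against.** The strongest reply is that nothing is lost. Every event starting after an infusion is still treatment-emergent under SAP 7.3.2; the protocol's cut-off of 56 days after the last dose leaves ample room for a 14-day interval. Such events are tabulated by preferred term, relationship and severity, and all adverse events are listed. Neither document calls the during-administration row a count of infusion reactions. A reader might infer that the plan undercounts these reactions outright. The documents do not support that: the undercount arises only if the row is used for a purpose the plan never gives it. Nor do they support reading the 0.5% to 0.7% as the share of reactions captured, or saying that the later period goes unexamined, since adverse events are monitored continuously.

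Causality must also be assessed for every event, and the grading in protocol Table 8 refers explicitly to temporal sequence. A related rash on day 8 would appear in the relatedness tables. A recognised serum sickness-like reaction should end treatment under protocol 8.3.2 and so reach the discontinuation listing. The onset statements are precautionary text about other antibodies, and protocol 5.1.2.2 reports no immunogenicity reactions with ALXN1210 to date.

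All of this stands, and it limits the point to how events are identified and presented. It does not remove the point. Relatedness tables do not separate infusion-associated events from other related events, and they rest on individual judgement. The discontinuation outputs omit reactions after which treatment continues. The protocol took these reactions seriously enough to require grading and to set a discontinuation criterion, yet no table brings them together.

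**Conclusion.** The point holds as a gap in identification. The only outputs defined by dosing time end with the infusion. The protocol's own onset periods run beyond it, and no term list, flag or window groups the later reactions. If the during-administration row were read as the measure of infusion-associated harm, it would undercount that harm.

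The size of that shortfall cannot be stated, because the documents give neither a reaction rate nor an onset distribution. The empty-row probabilities above show only that the effect could be visible with about 55 patients, and they depend wholly on the assumed r and s. The primary analysis is not affected. This is a cheap and worthwhile improvement to descriptive safety reporting.

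**What to change.** In SAP 7.3.2.1 and 7.3.2.5, with protocol 15.9.1 aligned, keep the during-administration row and listing. Add a pre-specified, medically reviewed preferred-term grouping for hypersensitivity, infusion-reaction and serum sickness-like events, built in the same way as the meningococcal search in SAP 9.4.7. Tabulate and list it by onset relative to the most recent infusion:

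1. during the infusion;
2. after the infusion ends, through a stated short window (for example 24 hours from its start, which is an assumption because the protocol gives no limit);
3. the remainder of days 1 to 14.

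A comparison with the period from day 15 to the next dose is optional. It should be confined to maintenance intervals, because the loading dose on Day 1 is followed by the next dose on Day 15 and leaves no such period. It should also be treated as descriptive, since the earliest intervals coincide with recovery from the acute illness.

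The inputs already exist: SAP 5.2.1 uses adverse event start date and time, and protocol 9.2 records the actual time of every dose. One new rule is needed for missing or partial start times, because SAP 9.4.6 settles only whether an event is treatment-emergent after the first dose. Under protocol 15.1, a change of this kind would not in itself require a protocol amendment.

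The cost is the term list and its medical review, that rule, one or two extra tables, and a higher reported count that will include some coincidental events. No change to dosing or clinical management is proposed.
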